2. STUDY OBJECTIVES AND ENDPOINTS

2.1 Objectives

2.1.1 Primary Objective

Phase I: To evaluate the safety of ixazomib when given in combination with romidepsin to establish the maximum tolerated dose (MTD) of this combination.

Phase II: To determine the complete response (CR) rate of this combination in relapsed/refractory PTCL.

2.1.2 Secondary Objectives

1. To determine the overall response rate (ORR)
2. To determine the duration of response (DOR)
3. To determine the time to next treatment (TTNT)

4. To determine the overall survival (OS)

2.1.3 Correlative/Exploratory Objectives

1. To examine TNFR2 and HR23B expression as predictive biomarkers
2. To biobank diagnostic biopsy specimens and other biologic specimens (i.e., blood, serum, plasma) for future correlative studies.

2.2 Endpoints

2.2.1 Primary Endpoint

Phase I: Dose limiting toxicities (DLTs) based on adverse event (AE) evaluation defined by CTCAE v4.03 of the combination of ixazomib and romidepsin.

Phase II: CR, defined as complete metabolic response recorded from first day of treatment until disease progression or initiation of new antineoplastic therapy, as per the Lugano response criteria.

2.2.2 Secondary Endpoints

- OR, defined as complete or partial metabolic response recorded from first day of treatment until disease progression/recurrence or initiation of new antineoplastic therapy, as per the Lugano response criteria.
- DOR, defined as time that measurement criteria are met for complete or partial metabolic response (whichever status is recorded first) until disease progression/recurrence or initiation of new antineoplastic therapy, as per the Lugano response criteria.
- TTNT defined as the date of initiation of treatment until death or the date of initiation of the next treatment.
- OS, defined as time from first day of treatment to time of death.

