
(including vorinostat, romidepsin, and belinostat) abolishes GATA-3 DNA binding in both TCL cell lines and primary samples and the expression of its gene targets. We have not observed any alteration in total GATA-3 expression or nuclear localization following HDACi treatment. In coupled immunoprecipitation and immunoblotting studies, we have demonstrated that HDAC inhibition regulates the extent of GATA-3 acetylation (data not shown). These innovative findings suggest that HDAC inhibition disrupts GATA-3 DNA binding and target gene expression. If so, this finding would have significant clinical implications, suggesting that HDAC inhibitors may overcome chemotherapy resistance in GATA-3-expressing T-cell lymphomas.

GATA-3 expression is not only NF- κ B dependent^{38,57}, but is also required for the homeostatic survival^{57,58}, differentiation⁵⁹, and migration⁶⁰ of conventional T-cell subsets. Consistent with its role in conventional T cells, we have previously shown that GATA-3 is an NF- κ B target gene in malignant T cells and confers their resistance to chemotherapy in a cell-autonomous manner³⁸. Not surprisingly, GATA-3 expression has both diagnostic and therapeutic implications⁴⁰, and its expression has successfully identified high-risk PTCL patients who are unlikely to achieve a remission with conventional chemotherapeutic agents⁴⁴. Therefore, the observation that ixazomib led to significant inhibition of both NF- κ B and GATA-3 in primary TCL specimens *ex vivo* and following one month of treatment in the single responder treated in this study is noteworthy. Consistent with our findings, Ravi et. al. observed that ixazomib induced apoptosis in multiple T-cell lymphoma cell lines and was associated with widespread changes in gene expression.

Proteasome inhibition is synergistic with other therapeutic strategies, including HDAC inhibition⁶¹, and likely overcomes mechanisms of chemotherapy resistance in T-cell lymphomas^{22,36}. While the median OS in rel/refr PTCL is <6 months^{7,62,63}, a subset of patients treated with romidepsin achieve a durable CR (>12 months), that is associated with prolonged OS¹².

Therefore, we propose a multi-center phase II study with ixazomib and romidepsin in patients with relapsed/refractory PTCL. Since this is a novel combination, the phase I endpoint is to determine the dose limiting toxicity and maximum tolerated dose and the phase II endpoint is to determine the CR rate of this combination.

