9.2.1 Duration of Response

Duration of overall response—the period measured from the time that measurement criteria are met for complete or partial response (whichever status is recorded first) until the date that recurrent or progressive disease is objectively documented (taking as reference for progressive disease the smallest measurements recorded since treatment started) or initiation of new antineoplastic therapy.

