9.2.4 Overall Survival

Overall survival is defined by the date of first treatment to date of death from any cause.

10. DRUG INFORMATION**10.1 Ixazomib (See investigator brochure for additional details) ⁸⁰**

Ixazomib is a reversible proteasome inhibitor. Ixazomib preferentially binds and inhibits the chymotrypsin-like activity of the beta 5 subunit of the 20S proteasome.

Ixazomib induced apoptosis of multiple myeloma cell lines in vitro. Ixazomib demonstrated in vitro cytotoxicity against myeloma cells from patients who had relapsed after multiple prior therapies, including bortezomib, lenalidomide, and dexamethasone. The combination of ixazomib and lenalidomide demonstrated synergistic cytotoxic effects in multiple myeloma cell lines. In vivo, ixazomib demonstrated antitumor activity in a mouse multiple myeloma tumor xenograft model.

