12.7.2 Analysis Plans for Secondary Objectives

ORR at one year will be summarized for the Efficacy population, including appropriate uncertainty. DOR in the Efficacy population will be summarized via Kaplan-Meier (KM) methods and confidence intervals, with time = 0 defined as the date of first response. TTNT and OS will also be summarized with KM methods, with time = 0 defined as the date of first dose of cycle 1.

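### Duration of response has no death event, so under the planned Kaplan-Meier analysis a responder who dies without progression or new therapy would by default be censored, and the DOR curve can only be the same or higher

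*Combined protocol and SAP*

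**What the plan says.** DOR is defined twice in the combined protocol and SAP.

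- Section 2.2.2, DOR bullet: from first meeting the criteria for complete or partial metabolic response "until disease progression/recurrence or initiation of new antineoplastic therapy, as per the Lugano response criteria".
- Section 9.2.1: from the same starting point "until the date that recurrent or progressive disease is objectively documented", "or initiation of new antineoplastic therapy".

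The two differ in wording: only 9.2.1 requires objective documentation. They agree in not listing death.

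On analysis, Section 12.7.2 says "DOR in the Efficacy population will be summarized via Kaplan-Meier (KM) methods and confidence intervals", with time zero at first response. It gives no censoring rule, no competing-risk method and no treatment of deaths.

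The other time-to-event endpoints do count death. Section 2.2.2 has "TTNT defined as the date of initiation of treatment until death or the date of initiation of the next treatment", and Section 9.2.4 has "Overall survival is defined by the date of first treatment to date of death from any cause".

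**The concern.** Kaplan-Meier needs every responder to leave the risk set either with an event or as a censored time. If death is not an event and no other rule is given, a responder who dies without progression or new therapy leaves as a censored time. The estimator then treats that response as if it would have gone on like those of the patients still at risk. A response that ended in death should not be credited with further duration.

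Such deaths are foreseeable. Section 10.2.6 lists infections and sepsis with romidepsin, and Section 5.6.2 describes potentially fatal progressive multifocal leukoencephalopathy with ixazomib. After the pre-cycle 5 scan, routine imaging is every 3 cycles (3 x 28 = 84 days) up to 24 months and every 6 cycles after that (Section 7.2.5), so a patient can die between scans.

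At stake is the reading of a named secondary objective. Sections 1.2 and 1.4 both point to romidepsin remissions of about a year or longer, so readers are likely to set the trial's DOR beside those. DOR is also one of the outcomes in the biomarker analysis of Section 12.7.3.

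**Working it through.** **1. Is there a figure in the plan to reproduce?** Not for DOR: no median, event count or precision is stated. The phase II figures can be reproduced, and they show what DOR does not touch. With at least 3 complete responses (CRs) in 18 to continue and at least 8 in 30 to succeed, the exact two-stage binomial gives 0.0685 at a CR rate of 0.15 (stated 0.068) and 0.872 at 0.35 (stated 0.87). Only CR counts enter.

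**2. Does another section supply the missing event?** The response table in Section 9.2 defines progression by FDG uptake and new lesions, not by death, so the reference to the Lugano criteria in 2.2.2 does not supply it as those criteria are reproduced here. Sections 9.2.1 and 12.7.2 do not supply it either.

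**3. Direction.** Take one data set and code the deaths in two ways. Each patient leaves at the same time under both codings, so the number at risk n is the same at every time. The curve is the product of (1 - d/n) over event times, where d is the number of events. Censoring deaths can only lower d or leave it unchanged, so each factor is equal or larger, and so is the product. This needs no distributional assumption.

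**4. A small constructed example.** Ten responders: progressions at 3, 5, 8 and 11 months, deaths without progression at 4 and 6 months, four still in response after 12 months.

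- Death as an event: 6 events in 10 with no earlier censoring, so the 12-month estimate is 4/10 = 0.40.
- Deaths censored: 9/10 x 7/8 x 5/6 x 4/5 = 0.525.

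Here q = 2/6 = 33%. The example shows the mechanism; it is not a forecast.

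**5. Size under a stated model.** Let L be the constant hazard of any response-ending event, death included, and q the share of those events that are deaths without progression or new therapy. With deaths censored, Kaplan-Meier targets hazard L(1-q). Hence:

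- survival S(t) becomes S(t)^(1-q);
- the median ln2/L becomes ln2/[L(1-q)], a ratio of 1/(1-q).

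The documents do not give q, so a range is shown. To put it in months, assume S(12) = 0.53 with death counted. This borrows the 53% of 19 patients in complete remission on romidepsin (Section 1.2) purely as an anchor. Then L = -ln(0.53)/12 = 0.0529 per month, and the median is 0.693/0.0529 = 13.1 months.

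| q (assumed) | Median ratio | 12-month estimate | Median (months) |
|---|---|---|---|
| 0% | 1.00 | 0.530 | 13.1 |
| 5% | 1.05 | 0.547 | 13.8 |
| 10% | 1.11 | 0.565 | 14.6 |
| 20% | 1.25 | 0.602 | 16.4 |
| 30% | 1.43 | 0.641 | 18.7 |

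A simulation with 11 responders (5,000 runs per value of q, administrative censoring assumed uniform over 12 to 24 months) agrees. The mean 12-month estimate is 0.53 with death as an event, and 0.57, 0.60 and 0.64 with deaths censored at q = 10%, 20% and 30%.

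**The case against.** **Censoring is inferred, not written.** This stands. A reader might infer that the plan instructs the analyst to censor deaths. It does not: censoring is the default that follows from the event list and Kaplan-Meier. An analyst might count deaths anyway, but nothing in the plan says so.

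**Overstatement is relative to another quantity.** Read literally, the endpoint is time to progression or new therapy among responders, and it could be defended as such. But it already counts a change of therapy, which is not progression, and no reason is given for leaving out death. Even if the omission is deliberate, 12.7.2 still has to say how deaths enter. A competing-risk analysis with cumulative incidence would be a legitimate alternative.

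**The size is unknown.** This stands too. It is tempting to say that one or two deaths would be some fixed percentage of events. The documents give neither the number of responders nor the number of response-ending events, and the two are not interchangeable because some responders will have no event. Nor does the statement "While the median OS in rel/refr PTCL is <6 months" in Section 1.4 supply a rate: it describes relapsed/refractory patients in general, not responders. The 53% anchor is for single-agent complete remissions, not complete plus partial responses to the combination.

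**There is mitigation.** Imaging is also required at suspected clinical progression (Section 7.2.5), patients who stop treatment without progression are followed every 3 months for 2 years (Section 7.4), and the deaths count in time to next treatment and overall survival. This should reduce undocumented lymphoma deaths and keeps deaths visible elsewhere. It does not correct the DOR curve.

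**Importance is limited.** A reader might infer that the efficacy conclusion is at risk. It is not: Section 12.1 decides on CR alone.

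**Conclusion.** The gap is confirmed in both definitions, and no other section closes it. The direction is certain relative to DOR with death as an event: the planned curve would be equal or higher, never lower.

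The size is conditional. Under a constant hazard the median rises by 5%, 11% and 25% at q = 5%, 10% and 20%. All three values of q are assumptions, and the effect is zero if no responder dies without progression or new therapy. The figures in months rest further on the borrowed 12-month anchor.

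The consequence is confined to a descriptive secondary endpoint and its use in the biomarker analysis. It is worth correcting because the remedy is small and the uncorrected estimate would look more durable than the data support.

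**What to change.** - In Sections 2.2.2 and 9.2.1, end DOR at the first of progression/recurrence, new antineoplastic therapy, or death from any cause. Use the same wording in both places, since only one now requires objective documentation.
- In Section 12.7.2, analyse that endpoint by Kaplan-Meier, and state that responders alive without an event are censored at their last disease assessment.

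If the sponsor prefers to keep death out of the definition, 12.7.2 should instead treat it as a competing risk and report cumulative incidence.

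The cost is a phrase in two definitions and a sentence in the analysis plan. Survival status is already collected (Section 7 calendar and Section 7.4), so no new data are needed. The downside is that the reported DOR may be slightly shorter. Sample size and the CR decision rule do not change.

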3. ELIGIBILITY CRITERIA

3.1 Inclusion Criteria

Subject must meet all of the following applicable inclusion criteria to participate in this study:

1. Written informed consent and HIPAA authorization for release of personal health information.
NOTE: HIPAA authorization may be included in the informed consent or obtained separately.
2. Age \geq 18 years at the time of consent.
3. ECOG Performance Status of 0-2 within 14 days prior to registration.
4. Histological confirmation of peripheral T-cell lymphoma (PTCL) and biopsy confirmation of disease relapse (after initial or any subsequent salvage therapy within 6 months of enrollment).
5. Documented disease progression after receiving at least one prior therapeutic regimen.

6. Prior cancer treatment must be completed at least 21 days prior to C1D1 or 5 times the half-life of the drug(s), whichever is greater, and the subject must have recovered from all reversible acute toxic effects of the regimen (other than alopecia) to \leq Grade 1 or baseline. Systemic steroids at a dose less than the equivalent of 10 mg/day of prednisone and inhaled, nasal, and topical steroids are permitted. Intermittent dexamethasone for the treatment of nausea/emesis is also permitted if it is not greater than 40 mg/month.
7. Demonstrate adequate organ function as defined in the table below; all screening labs to be obtained within 28 days prior to registration.

System	Laboratory Value
Hematological	
Absolute Neutrophil Count (ANC) ¹	$\geq 1000/\text{mm}^3$
Platelets (Plt) ²	$\geq 75,000/\text{mm}^3$
Renal	
Calculated creatinine clearance	≥ 30 cc/min using the Cockcroft-Gault formula
Hepatic	
Bilirubin	$\leq 1.5 \times$ upper limit of normal (ULN), (exception of Gilbert disease)
Aspartate aminotransferase (AST)	$\leq 3 \times$ ULN, if known hepatic involvement then $\leq 5 \times$ ULN
Alanine aminotransferase (ALT)	$\leq 3 \times$ ULN, if known hepatic involvement then $\leq 5 \times$ ULN
¹ ANC: GCS-F is not allowed to meet ANC criteria. Subjects with significant marrow involvement will be discussed on a case-by-case basis with the Sponsor Investigator.	
² Platelets: Platelet transfusion not allowed within 3 days of blood draw.	

8. Females of childbearing potential must have a negative serum pregnancy test within 14 days prior to registration. **NOTE:** Females are considered of childbearing potential unless they are surgically sterile (have undergone a hysterectomy, bilateral tubal ligation, or bilateral oophorectomy) or they are naturally postmenopausal for at least 12 consecutive months
9. Females of childbearing potential and males must be willing to abstain from heterosexual activity or to use 2 forms of effective methods of contraception from the time of informed consent until 90 days after treatment discontinuation. The two contraception methods can be comprised of two barrier methods, or a barrier method plus a hormonal method.
10. Males must be willing to abstain from donating sperm or semen from the time of informed consent until 90 days after treatment discontinuation.
11. The subject must have the ability to understand and comply with study procedures for the entire length of the study, as determined by the treating physician or protocol designee.

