9. CRITERIA FOR DISEASE EVALUATION

Responses will be performed in accordance with the Revised Lugano classification staging system for non-Hodgkin's Lymphoma.

Evaluable for toxicity. All patients will be evaluable for toxicity from the time of their first treatment with study drug.

Evaluable for objective response. Only those patients who have measurable disease present at baseline, have received at least 1 cycle(s) of therapy, and have had their disease re-evaluated will be considered evaluable for response. These patients will have their response classified according to the definitions stated below.

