9.2 Definitions for Response Evaluation

Revised Criteria for Response Assessment ⁷⁹	
Response and Site	PET-CT-Based Response
Complete Lymph nodes and extralymphatic sites	Complete metabolic response Score 1, 2, or 3 with or without a residual mass on 5PS* It is recognized that in Waldeyer's ring or extranodal sites with high physiologic uptake or with activation within spleen or marrow (eg, with chemotherapy or myeloid colony-stimulating factors), uptake may be greater than normal

Nonmeasured lesion Organ enlargement New lesions Bone marrow	mediastinum and/or liver. In this circumstance, complete metabolic response may be inferred if uptake at sites of initial involvement is no greater than surrounding normal tissue even if the tissue has high physiologic uptake Not applicable Not applicable None No evidence of FDG-avid disease in marrow
Partial Lymph nodes and extralymphatic sites Nonmeasured lesion Organ enlargement New lesions Bone marrow	Partial metabolic response Score 4 or 5* with reduced uptake compared with baseline and residual mass(es) of any size At interim, these findings suggest responding disease At end of treatment, these findings indicate residual disease Not applicable Not applicable None Residual uptake higher than uptake in normal marrow but reduced compared with baseline (diffuse uptake compatible with reactive changes from chemotherapy allowed). If there are persistent focal changes in the marrow in the context of a nodal response, consideration should be given to further evaluation with MRI or biopsy or an interval scan
No response or stable disease Lymph nodes and extralymphatic sites Nonmeasured lesion Organ enlargement New lesions Bone marrow	No metabolic response Score 4 or 5* with no significant change in FDG uptake from baseline at interim or end of treatment Not applicable Not applicable None No change from baseline
Progressive disease Lymph nodes Extranodal lesions Nonmeasured lesion New lesions Bone marrow	Progressive metabolic disease Score 4 or 5* with an increase in intensity of uptake from baseline and/or New FDG-avid foci consistent with lymphoma at interim or end-of-treatment assessment None New FDG-avid foci consistent with lymphoma rather than another etiology (eg, infection, inflammation). If uncertain regarding etiology of new lesions, biopsy or interval scan may be considered New or recurrent FDG-avid foci

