The (up-to) 18 patients at the estimated MTD will comprise the interim analysis of a 2-stage phase II study of efficacy of this dual-agent therapy. The patients will be evaluated for CR and comprise an interim futility analysis for the dual-agent therapy. If at least 3 of the (up-to) 18 patients show CR, we will proceed to the second stage of the phase II. If the phase I stage terminates with 18 patients at the estimated MTD, this corresponds to an empiric CR rate of $3/18=17\%$; if the phase I stage terminates with 16 or 17 patients at the estimated MTD (because total enrollment hits 36 patients), this corresponds to an empiric CR rate of 19% or 18%.

Phase II. Upon successful completion of the phase 1 design/interim efficacy analysis, we will transition to a final evaluation of the efficacy of the dual-agent ixazomib and romidepsin at the MTD. We will test the null hypothesis that the rate of CR is 15%, which is the expected CR rate for romidepsin (see section 1.2). Additional patients will be enrolled to the dual-agent MTD estimated from the phase I step, for a total of up to 30 patients at the MTD (up to 18 from phase 1 + 12 from phase II). When all patients have been followed for response status, if at least 8 patients demonstrate CR, we will declare the dual-agent MTD to be sufficiently efficacious. With 30 patients, this is an empiric CR rate of 27%. If the true CR rate is 0.15, this will occur with probability 0.068 (type I error); if the true CR rate is 0.35, this will occur with probability 0.87 (power). Section 12.3 summarizes the statistical performance of this design in more detail. In the unlikely scenario that fewer than 18 patients are at the MTD after the phase I terminates (the probabilities of this occurring are in Table 12.3.1), we will have slightly reduced power to detect a high CR rate (see Table 12.3.2).

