12.6 Assessment of Efficacy

Only patients who have received at least 1 cycle(s) of therapy, and have had their disease re-evaluated will be considered evaluable for response. Non-evaluable patients will be replaced.

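### Eligibility does not require measurable or FDG-avid disease at screening, and the plan conflicts on whether baseline disease is a condition of the primary CR analysis

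*Combined protocol and SAP*

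**What the plan says.** **Entry.** Criterion 5 of Section 3.1 reads "Documented disease progression after receiving at least one prior therapeutic regimen". It does not say that the progression must follow the latest regimen. Criterion 4 asks for biopsy-confirmed relapse with a six-month limit, but not that the biopsy postdate the last therapy. PET/CT is a mandatory screening procedure (Section 7 calendar, Section 7.1.1), yet no result is needed for entry. Nothing in 3.1 or 3.2 mentions measurable or FDG-avid disease.

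**Evaluability.** Section 9 limits response evaluation as follows: "Only those patients who have measurable disease present at baseline", together with one cycle of therapy and a re-evaluation. Section 12.6 says: "Only patients who have received at least 1 cycle(s) of therapy, and have had their disease re-evaluated will be considered evaluable for response". It has no baseline-disease condition, and it adds that non-evaluable patients are replaced. Section 12.4 defines the Efficacy population as those treated at the estimated MTD, up to 30. Section 9.2.2 takes the CR rate over all subjects.

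**Response.** For nodal and extralymphatic sites, Section 9.2 defines complete metabolic response as "Score 1, 2, or 3 with or without a residual mass on 5PS".

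**Test.** Section 12.1: "We will test the null hypothesis that the rate of CR is 15%, which is the expected CR rate for romidepsin". The interim rule is "If at least 3 of the (up-to) 18 patients show CR, we will proceed to the second stage of the phase II", and the final rule is "if at least 8 patients demonstrate CR, we will declare the dual-agent MTD to be sufficiently efficacious".

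**The concern.** A single-arm CR test assumes that each counted patient had disease that could be seen to disappear on the scan used to score response. Here entry does not guarantee that, and the sections that define the analysis set disagree about it.

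Two kinds of patient matter:

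- **No measurable disease at baseline**, for example after a response to salvage therapy given since the relapse biopsy. Section 9 makes this patient non-evaluable. Sections 12.6, 12.4 and 9.2.2, read alone, count the patient.
- **A residual mass that is already PET-negative.** If a mass on CT counts as measurable, this patient passes Section 9 as well as 12.6. The patient then meets the nodal CR criterion at the scan before cycle 3 if nothing changes.

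Such patients would add CRs that say nothing about the study drugs, both to the interim count (3 needed) and to the final count (8 needed). With 30 patients and a threshold of 8, one such patient matters.

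**Working it through.** **Inputs.** From Section 12.1: n1 = 18, continue if at least 3 CRs; n2 = 12, success if at least 8 CRs among 30; null rate 0.15, alternative 0.35. Stated type I error 0.068, power 0.87. The number k of patients already PET-negative at baseline is not in the documents. It is an assumption, taken here as 0, 1 or 2.

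**Step 1: reproduce the plan.** With X1 ~ Bin(18, p) and X2 ~ Bin(12, p),

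P(success) = Σ over x ≥ 3 of P(X1 = x) · P(X2 ≥ 8 − x).

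- p = 0.15: 0.0685 (stated 0.068); futility stop 0.480 (Table 12.3.2: 48%).
- p = 0.35: 0.872 (stated 0.87); futility stop 0.024 (table: 2.4%).

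The design figures are correct.

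**Step 2: count k such patients as certain CRs.** Put k1 in stage 1 and k2 in stage 2, with all others at 0.15. Then Y1 ~ Bin(18 − k1, 0.15), Y2 ~ Bin(12 − k2, 0.15), and success needs Y1 ≥ 3 − k1 and Y1 + Y2 ≥ 8 − k1 − k2.

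| k1 | k2 | Futility stop | P(declare efficacy) |
|---|---|---|---|
| 0 | 0 | 0.480 | 0.068 |
| 1 | 0 | 0.252 | 0.132 |
| 0 | 1 | 0.480 | 0.129 |
| 2 | 0 | 0.074 | 0.235 |
| 1 | 1 | 0.252 | 0.232 |
| 0 | 2 | 0.480 | 0.221 |

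Check of the futility figure for one patient in stage 1: P(Y1 ≤ 1) = 0.85^17 + 17 × 0.15 × 0.85^16 = 0.063 + 0.189 = 0.252.

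**Step 3: relax the certain-CR assumption.** Suppose one stage 1 patient has a 50% chance (assumed) of still being CR when scanned. If not CR, the design behaves like the 17 + 12 row of Table 12.3.2, at 0.0572. The result is 0.5 × 0.1323 + 0.5 × 0.0572 = 0.095.

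**Step 4: the same patient under each reading.** One stage 1 patient with no measurable disease at baseline, others at 0.15:

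| Reading | Handling | P(declare efficacy) |
|---|---|---|
| Section 9 plus the 12.6 replacement rule | Not evaluable, replaced | 0.068 |
| Section 9 for scoring, all-subjects denominator of 9.2.2 | Kept among the 30, not a CR | 0.057 (power 0.84) |
| 12.6, 12.4 and 9.2.2 without Section 9 | Counted, certain CR | 0.132 |

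A PET-negative residual mass that counts as measurable gives 0.132 even when Section 9 is applied.

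**The case against.** The strongest reply is that Section 9 already deals with the main case. Its rule and the one in 12.6 both state necessary conditions, so they can be applied together, and 12.6 may be only a shortened restatement. A patient without measurable disease is then replaced, and the error rate is unchanged. This stands. A reader might infer that 12.6 overrides Section 9 because it sits in the statistical section, and hence that patients in remission will be scored CR. No passage gives 12.6 that precedence. Equally, none gives it to Section 9, and 12.4 and 9.2.2 point the other way.

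The route into the trial is also narrow. Relapse must be biopsy-confirmed within six months, and salvage, response, washout and recovery from toxicity must all fit between that biopsy and enrolment. The population is described throughout as relapsed or refractory. Nothing suggests that such entries would be common.

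Nor is a CR certain. The CR row in 9.2 mentions sites of initial involvement, though only when describing high physiologic uptake. Section 9.2.2 asks for confirmed CR under a cited classification that cannot be consulted here. Section 1.4 puts median survival in relapsed or refractory disease below 6 months, so early relapse is plausible; Step 3 shows the effect.

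One might add that the 15% null came from patients with active, assessable disease. Sections 1.2 and 12.1 give only the rate, so that argument is not used.

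The reply does not cover the PET-negative residual mass, because measurable is never defined.

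**Conclusion.** The concern holds as a gap in eligibility joined to a conflict over the analysis set. Sections 3.1 and 3.2 do not require measurable or FDG-avid disease, and Section 9 disagrees with 12.6, 12.4 and 9.2.2 on whether baseline disease is a condition of the primary CR analysis. The undefined term in Section 9 leaves a second opening even if that conflict is settled in its favour.

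The size is conditional. If such patients are counted, each is a certain CR and all others are at 15%, the chance of declaring efficacy rises from 0.068 to about 0.13 with one and to 0.22–0.24 with two. One in stage 1 also cuts futility stopping under the null from 48% to 25%. With Section 9 and replacement applied to patients without measurable disease, it stays 0.068. The documents therefore do not support saying that the type I error is inflated as planned. They support saying that it depends on which section is followed and on how many such patients enter.

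A reader might also infer that criterion 5 must be tied to the most recent regimen. That is not needed to close the gap, and it would exclude patients who stopped their last regimen in partial response with avid disease remaining.

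**What to change.** 1. **Section 3.1:** add a criterion requiring at least one FDG-avid lesion, 5PS score 4 or 5, on the screening PET/CT, with the scan done after the most recent therapy. The timing needs stating: the scan may be up to 28 days before registration, while prior treatment may end 21 days before C1D1, so a permitted scan can predate the end of that treatment.
2. **Sections 9, 9.2.2, 12.4 and 12.6:** use this same baseline condition in all four, in place of the undefined term in Section 9, and state one denominator and one replacement rule. Copying Section 9 into 12.6 as it stands would leave the PET-negative residual mass unresolved, and some patients would still be treated and then replaced.
3. **Criterion 5:** leave unchanged.

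The cost is amendment wording. The screening PET/CT is already mandatory, so no procedure is added, although some scans may have to be timed later. A few patients without FDG-avid disease become ineligible, but a CR in them could not be interpreted. The decision rule, sample size and stated operating characteristics do not change.
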